Previous weight loss interventions conducted by the P.I., [name], have focused on disease prevention and health promotion in various populations. The current and previous NIH funded randomized controlled weight loss trials (Comprehensive Lifestyle Intervention Program for Knee Osteoarthritis Patients, R01AG050725; Feasibility of An Exercise and Dietary Intervention in Men on Prolonged Androgen Deprivation Therapy, IDEA-P trial; R03CA16296901) have demonstrated a strong interdisciplinary team with extensive experience in design/delivery of weight loss program (**Figure 2**). The Co-I of this proposed project, [name], is a nationally recognized investigator in health disparities. Her research with underserved populations established the expertise and capability to conduct studies in disease prevention, health disparities, and improving access in underserved areas, including a faith-based weight loss program in Appalachian states (The Walk by Faith Trial; U54 CA153604) and the Rural Interventions for Screening Effectiveness (RISE; R01 CA196243). The RISE Project recruited 1039 participants from rural Ohio and Kentucky who had complete data on height and weight and agreed to be contacted about opportunities for future research. About 573 of them live in northwest rural Ohio, and 330 had a $BMI \geq 25 \text{ kg/m}^2$. We anticipate at least 40% of these participants would be willing to participate in this study.

[figure not shown]

Figure 2. 12-week lifestyle intervention effect on weight loss, the IDEA-P trial ([name])

C RESEARCH DESIGN AND METHODS

C.1 Overall strategy.

This study is a single-blind, 2-arm randomized controlled pilot study designed to determine the feasibility and preliminary efficacy of a 15-week telephone-based weight loss in obese rural populations. Up to 50 obese rural Ohio residents will be randomly assigned to a 15-week telephone-based weight loss group (n=30) or active control group (up to 20). The primary outcome of this trial is the feasibility of a 15-week telephone-based weight loss intervention. The exploratory outcomes include changes in weight, body composition, lipid profiles, and inflammatory markers (CRP, IL-6, and TNF- α). Exploring the efficacy of the telephone-based intervention on weight loss, body composition, lipid profiles, and inflammatory markers will provide preliminary effect estimates for future larger-scale randomized controlled trial in rural populations.

C.2 Research Team

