Eligible participants will be grouped by their residency locations (e.g., county, geographic region) to schedule in-person assessments (baseline and 15-week). To optimize retention and maintain data fidelity, all assessments

will be obtained on-site at community locations (e.g., library, Area Health Education Center) close to participants' homes by trained study staff.

C.3.c Recruitment

We will recruit up to 50 overweight/obese rural residents through social media (i.e., Facebook), flyers, and a list of participants from a previous study (The RISE Project). We anticipate to screen 9-15 individuals per week and recruit 4-5 participants per month.

C.3.d Randomization

Participants will be randomized to either the weight loss intervention group (Telephone-based health counselling) or the active control group (Health education) using block randomization in 4-5 waves. Every 6-12 participants consented and enrolled, one wave will be formed. For each wave, participants will be assigned to either weight loss (n=30) or active control group (up to 20 participants).

C.3.e Informed consent process

After confirming eligibility for the trial, each participant will be given a unique study number. The research staff (see **table 1** for details) will explain all aspects of the study in lay language and answer all the candidate's questions regarding the study. The individual will be asked to provide written informed consent to participate in the study. If an eligible participant refuses to provide written consent, the research staff will not proceed with the baseline assessment. The research staff will follow talking points that will outline all of the requirements of the study and will cover the content of the informed consent form. The participants will be given a copy of the informed consent document for their records and afforded the opportunity to ask questions and have them answered to their satisfaction. Once the individual fully understands each element of the consent and the study, including the purpose, requirements, risks, confidentiality, right to withdraw, and contact person, then he/she will be asked to provide consent. The screening process will take approximately 5 minutes, and the informed consent process could take up to 15 minutes to complete.

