Outcome assessments will be obtained at baseline and 15 weeks later at in-person visits by research staff blinded to treatment group assignment. All outcome assessments will be conducted at a community center or public location convenient to the participant. Each outcome measure will be collected through paper or online survey (through REDCap) and stored in REDCap (Research Electronic Data Capture).

C.7.a Primary Outcome: feasibility and acceptability

Completion rate and participation of the weekly telephone counseling session will be measured to evaluate the feasibility and acceptability of the 15-week telephone-based weight loss intervention.

C.7.b Secondary Outcome Assessment

Self-reported questionnaires and objective measures by research staff will be used (**Table 3**).

Table 3. Assessment Approach

Assessment	Approach	Time
Weight, height	Research staff using weight scale	2 mins
Body composition	Research staff using Styku 3D body scanner	10 mins
Hydration status	Research staff using urine specific gravity	3 mins
Lipid: Total cholesterol (TC), triglycerides (TG), high-density lipoprotein cholesterol (HDL-C), and low-density lipoprotein cholesterol (LDL-C)	Research staff (with training) using Cholestech LDX	3 mins
Inflammatory markers: C-reactive protein (CRP), Interleukin (IL)-6, TNF- α	Research staff (certified phlebotomists) conducting blood draw	5 mins
Objectively measured physical activity	Participants will wear ActivPAL for 7 days	--
IPAQ Leisure-Time Exercise Questionnaires	Self-reported via paper or online survey	5 mins
Diet diary (developed by NCI)	Self-reported via paper for 7 days	--
Healthy eating and weight SE questionnaires	Self-reported via paper or online survey	5 mins
Multi-dimensional Self-Efficacy scales	Self-reported via paper or online survey	5 mins
Social Support Inventory for Physical Activity	Self-reported via paper or online survey	5 mins
Social Support Inventory for Healthy eating	Self-reported via paper or online survey	5 mins
Physical Fitness	Research staff (with training) using standard protocols	15 mins

1. Anthropometric assessment

Body weight (kg) and height (cm) will be measured to calculate BMI (kg/m^2).

2. Body composition

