We considered using a standard measure of body composition using Dual-energy X-ray absorptiometry (DXA) but opted not to as this is likely to add the burden of travel to facilities equipped with DXA. However, we will assess body composition using a 3-D Styku body scanner, which is portable to rural community-settings and can provide valid and reliable data on body composition. Together with using Cholestech LDX to evaluate participants' lipid profiles, the proposed study is innovative to test new point-of-care approaches to assess disease risk factors in rural populations.

D DATA HANDLING AND ANALYSES

D.1. Outcome Analysis Plan

D.1.a Primary outcome

The feasibility of completing the study is defined as the percentage of enrolled participants who complete the study. If we observe an 80% completion rate in the weight loss intervention group (n=30), the 85%, 90%, and 95% confidence intervals (CIs) for the completion rate would be (69.5, 90.5), (68.0, 92.0), and (65.7, 94.3), respectively. If the true completion rate is 80%, we have 95% power to rule out the unacceptable 50% completion rate with 95% confidence (one-sided).

The acceptability of the weight loss intervention is the percentage of participants in the weight loss intervention group who engage at least 75% of the weekly telephone counseling session. Intervention-related adverse events, satisfactory, and other feasibility assessments, such as the percent of initial contact to enrollment, reasons for consent refusal, barriers to adherence to weekly goals, and reasons for drop-out will also be assessed.

D.1.b Secondary outcome

Significance test for the preliminary efficacy of the lifestyle intervention will quantify the difference in means using repeated measures analysis of variance (ANCOVA) statistical model to adjust baseline values and control for the effect of age. The sample size of 30 participants in the weight loss group and at least 15 in the active control group is feasible to recruit for a pilot/preliminary efficacy study that accounts for a projected attrition rate of 20% yet also still provides adequate power to detect meaningful, moderate to large effect size (0.54-0.72) on weight loss, body composition, inflammatory markers, and lipid profiles.

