Analyses will be conducted using the intention to treat principle with last value carried forward approach used to account for data missing due to participant attrition. Exploratory analyses will compare outcomes including weight loss, changes in body composition, changes in physical activity and dietary intake, changes in lipid profiles and inflammatory biomarkers between the telephone-based weight loss group and the active control group. We will also examine whether social support and self-efficacy changes among participants from the weight loss group. These exploratory analyses will provide effect size estimates to inform the development of a large-scale phase II randomized controlled lifestyle weight loss intervention trial.

D.2. Data Management

As mentioned above, we will use REDCap as our data entry system. It will be used to store the baseline and follow-up questionnaires, will work directly with the OSU CCTS Research Informatics Services Core and will be

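### The efficacy model in D.1.b is named as two different analyses, and it leaves out the wave within which participants are randomised

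*Combined protocol and SAP*

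**What the plan says.** Section D.1.b (Secondary outcome) has one sentence on the efficacy model. It describes a "repeated measures analysis of variance (ANCOVA) statistical model to adjust baseline values and control for the effect of age". No other section names or corrects the model, and the only adjustments listed are baseline and age.

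Section C.7 fixes the time points: "Outcome assessments will be obtained at baseline and 15 weeks later". There is therefore one value after baseline per participant.

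Section C.3.d describes the allocation as "using block randomization in 4-5 waves. Every 6-12 participants consented and enrolled, one wave will be formed", with assignment to arms made within each wave. It gives no block size and no ratio per wave. D.1.b plans for "30 participants in the weight loss group and at least 15 in the active control group", and elsewhere the control arm is capped at 20.

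Section C.1 sets the status of these endpoints: "The exploratory outcomes include changes in weight, body composition, lipid profiles, and inflammatory markers". D.1.b states what they are for: "These exploratory analyses will provide effect size estimates to inform the development of a large-scale phase II randomized controlled lifestyle weight loss intervention trial".

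**The concern.** ANCOVA is not an abbreviation of repeated-measures ANOVA. With two time points, the group-by-time test in a repeated-measures ANOVA is the comparison of mean change between arms, and baseline is one of the outcomes. In ANCOVA the 15-week value is the outcome and baseline is a covariate. Under randomisation both target the same mean difference, but in a given data set they give different estimates and interval widths.

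The rest of D.1.b does not resolve the matter. Adjusting for baseline suggests ANCOVA, while the exploratory comparisons are described as changes, which suits a change-score analysis. Two analysts could follow the text and hand different effect sizes to the designers of the next trial. The choice could also be made after the data are seen.

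The second part is that allocation is blocked within waves but the model ignores wave. If waves differ in the 15-week outcome beyond what baseline explains, the blocking makes the estimate more precise than the model recognises. Standard errors are then too large and the test is conservative.

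**Working it through.** **The plan's own figure.** D.1.b says effects of 0.54 to 0.72 are detectable with adequate power, but for this analysis gives no power, alpha, sidedness or correlation r between baseline and 15 weeks. The range cannot be reproduced from stated inputs. As an unadjusted two-sided 5% comparison of 30 and 15, power is 39% at 0.54 and 61% at 0.72. Under assumed inputs ANCOVA can match the range. With 24 against 12 completers, one-sided 5% and 80% power, the unadjusted detectable effect is 0.898. Multiplying by √(1−r²) gives 0.719 at r = 0.6 and 0.539 at r = 0.8. The change-score analysis on the same inputs gives about 0.80 and 0.57. The match was found by trying assumptions, so it does not show which model was meant.

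**Model name: variance.** With outcome SD 1 at both visits:
- Change score: variance factor 2(1−r)
- ANCOVA: variance factor 1−r²
- Ratio of ANCOVA to change score: (1−r²)/[2(1−r)] = (1+r)/2, which is 75% at r = 0.5, 85% at 0.7 and 95% at 0.9

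**Model name: power and disagreement.** These come from simulation at two-sided 5% with effect d = 0.72 and no wave effect. ANCOVA is fitted on arm, baseline and age, and the change score on arm and age. The last column is the SD, across trials, of the difference between the two estimates obtained from the same trial.

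| Arms | r | ANCOVA power | Change-score power | SD of difference |
|---|---|---|---|---|
| 30:20 | 0.5 | 79.1% | 67.7% | 0.149 |
| 30:20 | 0.7 | 92.1% | 87.9% | 0.092 |
| 30:20 | 0.9 | >99% | >99% | 0.034 |
| 30:15 | 0.5 | 70.7% | 59.9% | 0.163 |
| 30:15 | 0.7 | 86.3% | 81.1% | 0.101 |
| 30:15 | 0.9 | >99% | >99% | 0.038 |

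The last column agrees with the approximation (1−r)√(1/n₁+1/n₀). For 30:20 at r = 0.5 this is 0.5 × √(1/30+1/20) = 0.144. For 30:15 it is 0.5 × √(1/30+1/15) = 0.158.

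**Wave.** These use 40,000 simulated trials per setting, r = 0.5, d = 0.72 and within-wave outcome variance 1. The layouts are assumed: five waves of 6:4 for 30:20, and three waves of 8:4 plus one of 6:3 for 30:15. Entries are power without wave, then with wave.

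| Wave variance | 30:20 | 30:15 |
|---|---|---|
| 0 | 79.0 → 78.6% | 71.0 → 70.6% |
| 0.02 | 78.2 → 78.6% | 70.1 → 70.4% |
| 0.05 | 77.2 → 78.5% | 69.0 → 70.5% |
| 0.1 | 75.9 → 78.8% | 67.3 → 70.6% |
| 0.3 | 68.7 → 78.3% | 60.1 → 70.2% |

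Without wave, type I error is 4.5% at wave variance 0.05, about 4% at 0.1 and about 3% at 0.3. With wave it is 4.8% to 5.2%. The model standard error without wave exceeds the true one by 3%, 5–6% and 14% at those three variances.

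If waves shift baseline as much as the outcome, the baseline covariate absorbs most of the effect. At wave variances 0.1 and 0.3 the gain from adding wave is then only 0.3 to 1.5 points.

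A separate simulation at r = 0.6, with 20% of residual variance due to wave, gave the same pattern. For 30:20, type I error was 3.2% without wave and 4.3% with it, and power 87.5% and 91.0%.

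**The case against.** The strongest reply is that the sentence says the model adjusts "to adjust baseline values and control for the effect of age". If baseline is a covariate in an analysis of change, the result is ANCOVA: moving baseline across the equation alters its own coefficient by 1 and leaves the arm coefficient, standard error and p-value unchanged. The contrasts above therefore arise only if an analyst treats subtraction as the baseline adjustment. That is the weaker reading, so the figures show the possible cost of the label, not the expected one. This is right as far as it goes. It does not remove the ambiguity, because a repeated-measures ANOVA with age as covariate is also a fair reading of the words.

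On wave, the reply is that the gain rests on an assumed variance. A value of 0.3 is 0.3/1.3 = 23% of total outcome variance, and nothing in the documents supports that much. This stands, and the benefit should not be oversold. Some difference between waves is plausible, because section C.9 has recruitment running from month 3 of Year 1 to month 7 of Year 2, but it is not established.

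It is also true that these outcomes are exploratory and that estimates from 45 to 50 people will be imprecise under either model.

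**Conclusion.** The concern holds on both parts. The efficacy model carries two names that denote different analyses, and it omits the factor within which allocation is blocked.

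The model name matters more if r is moderate: about 11 points of power and a 0.15–0.16 SD spread between the two estimates at r = 0.5, falling to almost nothing at r = 0.9. A spread of 0.15 is not trivial beside a planned range of 0.54 to 0.72. The wave omission is a lesser matter: small unless waves differ markedly, and conservative when they do.

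The feasibility conclusion does not change, and neither model is invalid under randomisation. The statement that leaving out wave causes no bias assumes a constant ratio in every wave, which C.3.d does not guarantee. With waves of 6 to 12, an exact 3:2 split is possible only in a wave of 10, and an exact 2:1 split only in waves of 6, 9 or 12. If the ratio varies, arm and wave become correlated, and including wave guards against that.

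The figures assume r, wave variance, wave layout and a two-sided 5% test. They take d as the effect in the analysed set: dilution from the approach in "Analyses will be conducted using the intention to treat principle with last value carried forward approach" is not modelled.

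**What to change.** In D.1.b, remove the repeated-measures label and state one model: ANCOVA of the 15-week value on arm, baseline value, age and wave, reporting the adjusted mean difference with its 95% CI.

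This is a one-sentence edit, best made before outcome data are seen. The wave term uses 3 or 4 of the 41 to 46 residual degrees of freedom (45 − 4 and 50 − 4, after intercept, arm, baseline and age). It costs about 0.4 points of power if waves do not differ. Randomisation and data collection stay as they are.

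### Does the unstated basis for the claim of adequate power at effects of 0.54-0.72 in D.1.b call for a change to the plan?

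*Combined protocol and SAP*

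**What the plan says.** D.1.b plans an ANCOVA of the efficacy outcomes "to adjust baseline values and control for the effect of age". It then justifies the numbers: "The sample size of 30 participants in the weight loss group and at least 15 in the active control group" is described as recruitable, as allowing for 20% attrition, and as giving "adequate power to detect meaningful, moderate to large effect size (0.54-0.72) on weight loss, body composition, inflammatory markers, and lipid profiles". Section C.1 allows up to 20 controls, so 15 is the floor.

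Missing data are handled under intention to treat, with "last value carried forward approach used to account for data missing due to participant attrition". Section C.7 fixes the visits: "Outcome assessments will be obtained at baseline and 15 weeks later at in-person visits".

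On status, C.1 states: "The exploratory outcomes include changes in weight, body composition, lipid profiles, and inflammatory markers". D.1.b closes its analysis text in the same spirit: "These exploratory analyses will provide effect size estimates to inform the development of a large-scale phase II randomized controlled" lifestyle trial.

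By contrast, D.1.a gives a numeric power (95%), a confidence level and a sidedness for the completion rate. D.1.b gives none of these for the efficacy outcomes.

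**The concern.** A detectable effect has no meaning until the error rate, power, analysed numbers, effect scale and, for ANCOVA, the baseline correlation are known. With no baseline correlation, 24 against 12 completers at 80% power would detect only about 0.90 SD one-sided at 5%, or 1.02 SD two-sided. Reaching 0.54-0.72 therefore needs something the text does not state.

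The analysis plan adds a second doubt. With staff-measured outcomes taken only at baseline and week 15, carrying the last value forward means carrying the baseline value. If 20% drop out of each arm, the analysed difference averages 0.8 of the effect among completers. A reader cannot tell which of the two the printed range describes. Someone sizing the later trial who confused them would be wrong by a factor of 1/0.8² = 1.56 in sample size. If the range was computed for completers, the planned analysis would also have somewhat less power than supposed.

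**Working it through.** **Inputs from the documents.** 30 intervention and 15 to 20 control participants; 20% attrition, hence 24 against 12 (or 16) completers; ANCOVA with baseline and age; last value carried forward; visits at baseline and week 15.

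**Inputs assumed.** Alpha 5%, 80% power, correlation r between baseline and week 15 of 0.6 to 0.8, effects in SDs of the week-15 value, attrition equal by arm and unrelated to outcome, no mean change in controls.

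**1. Reproducing 0.54-0.72.** Power is the upper tail of a noncentral t with noncentrality d / [√(1−r²) · √(1/n₁+1/n₂)] and n₁+n₂−4 degrees of freedom.

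At r = 0.6, √(1−r²) = 0.8; at r = 0.8 it is 0.6. Since 0.72/0.8 = 0.54/0.6 = 0.90, the two ends of the range are one unadjusted effect of 0.90 seen at two correlations. Any design with an unadjusted detectable effect near 0.90 will therefore fit:

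| Assumed setting, 80% power | r = 0.8 | r = 0.6 |
|---|---|---|
| 24 v 12 completers, one-sided 5%, noncentral t | 0.539 | 0.719 |
| 30 v 15, no dropout, two-sided 5%, noncentral t | 0.544 | 0.726 |
| 24 v 16 completers, two-sided 5%, normal approximation | 0.543 | 0.723 |
| 30 v 15, carry-forward, two-sided 5%, simulated, difference as analysed | 0.529 | 0.716 |

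Third row: (1.960 + 0.842) × √(1/24 + 1/16) = 0.904, times 0.6 or 0.8.

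Fourth row: true effects of 0.662 and 0.895, each multiplied by 0.8.

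Four different readings fit, so the source of the range cannot be identified from the text.

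**2. What carry-forward does under the first reading.** The analysed difference becomes 0.8 × 0.72 = 0.576, or 0.8 × 0.54 = 0.432. One-sided power at 5%:

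| | 0.72, r = 0.6 | 0.54, r = 0.8 |
|---|---|---|
| 24 v 12 completers, formula | 80.1% | 80.1% |
| 24 v 12 completers, simulated | 78% | 78% |
| 30 v 15, carry-forward, simulated | 74.5% | 75.5% |

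The formula ignores chance covariate imbalance between arms and is slightly optimistic. Comparing simulation with simulation, carry-forward costs about 2.5 to 3.5 points, not 5. With 20 controls, simulated one-sided power under carry-forward is about 82-83%.

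**3. How far the answer moves with the assumptions.**
- Two-sided, carry-forward power is 62-63% with 15 controls and 71-73% with 20.
- One-sided with 15 controls, dropout near 10% gives about 82-83% and near 30% about 68-69%.
- Under carry-forward with 15 controls, 80% power at 0.72 and 0.54 needs r of 0.67 and 0.83 one-sided, or 0.76 and 0.87 two-sided. If r were 0.90, two-sided power at 0.54 would be about 89%.
- If the range were in SDs of change, 24 against 12 completers would detect 0.78-0.86 one-sided (r from 0.5 to 0.85), which is outside it.

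**4. Limits of any reconstruction.** The range is attached to four outcome families and may run across outcomes, not correlations. For weight, C.4.d has intervention participants record it weekly and C.5 encourages controls to monitor it. The plan does not say whether such a record could be the last value. If it could, the factor 0.8 need not hold for weight.

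**The case for a change.** The best argument for acting is that the omission is real and cheap to repair. D.1.a shows that the authors can state power, confidence and sidedness when they choose to. D.1.b plans a significance test, and a null result is hard to read without knowing what the trial could detect. The closing text sends effect sizes forward to a larger trial, where the 0.8 factor would matter. One sentence would settle it, with no extra participants.

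The omission stands, and so does the arithmetic on carry-forward. The consequence does not follow. The later trial will draw on the estimates this pilot observes, produced by a stated analysis on a stated set, and not on the planning range of 0.54-0.72. A null result is read from its estimate and confidence interval, which need none of the missing inputs. D.1.b states no numeric power, so there is no promised figure that the design can be shown to miss. The shortfall to 75% appears only after one of several fitting reconstructions is chosen and the control arm is held at its minimum.

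**Conclusion.** No change follows. D.1.b leaves out the inputs behind 0.54-0.72, so the claim is uncheckable, but ordinary inputs recover it and no arithmetic slip is shown. Conditional on one-sided 5%, r of 0.6 to 0.8, equal 20% attrition unrelated to outcome, no control drift and baseline values carried forward, power at the printed effects is about 75% with 15 controls and 82-83% with 20. Read instead as the two-sided difference after carry-forward, the range is met at 80% power with 30 against 15.

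The claim carries little weight in this pilot. Efficacy is exploratory, no go/no-go rule refers to it, and the primary completion-rate calculation does not use it. Supplying the inputs would leave recruitment, the analysis and the interpretation of the primary aim as they are. It is a reporting gap of the kind an analyst fills by giving estimates with confidence intervals and saying which participants they cover.

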alternative exercise options, and provide simple tips for proper exercise form. These videos have been successfully implemented to facilitate home-based exercise in prior lifestyle interventions led by the investigative team. Each week participants will gradually increase their exercise duration and intensity in increments of 10-30 min until attaining the target physical activity volume goal.

C.4.d Behavioral component

Each week, participants will receive a 30-45 minute telephone counseling session that provides behavioral change techniques tailored to rural populations using the contemporary principles of cultural-tailoring and Social Cognitive Theory (105), and focus on motivation, relapse prevention, emotional distress, time management, and overcoming barriers. Each session will include a review of the previous week's activity, planned weekly lessons, dietary and exercise goals for the subsequent week, and strategies tailored to each participant to improve self-efficacy, social support, and overcome barriers. Additionally, group messages following the weekly telephone counseling is integrated with the behavioral component to promote independent adherence to lifestyle modification.

Participants will also receive a physical activity tracker (e.g., Fitbit) and a weight scale. Participants will learn how to use the Fitbit and will wear it during the entire study period. Participants will learn how to conduct self-measurements and record body weight each week, as well as set up MyFitnessPal (or using paper log) to self-monitor dietary intake and physical activity throughout the 15-week study period.

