The objective of the behavioral component is to promote increased self-efficacy and social support for lifestyle modifications and gradually facilitate participants' transition toward successful independent self-regulation of a healthy diet and physical activity. The behavioral component focuses upon the acquisition and practice of self-regulatory skills in conjunction with a continuous problem-solving model of behavior change to empower participants to exert greater control over their behavior, cognition, and environment. The behavioral component is designed to: a) increase health knowledge of the benefits of physical activity and dietary modifications; b) enhance self-efficacy and positive outcome expectancies through the promotion of a series of successful experiences in changing exercise and eating behavior; and c) improving self-regulation of exercise and eating behaviors through the use of goal-setting, self-monitoring, stimulus control, cognitive restructuring, and barrier problem-solving strategies. The efficacy of this approach for promoting adoption and maintenance of exercise and dietary behavior change has been demonstrated in prior randomized controlled trials that [name] has served as principal and co-investigator on other studies (106-109).

C.5 Active Control Group

At the beginning of the study, participants randomized to the active control arm will receive education brochures (will be submitted in the first amendment) describing the American Institute for Cancer Research physical activity and dietary guidelines. Participants will be asked to meet the 2018 Physical Activity Guidelines for Americans (150 min/week of moderate-intensity exercise or 75 min/week of vigorous exercise), and increase fruit and vegetable intake, reduce fat intake, reduce sugary drink, increase consumption of whole grain, and increase water intake. An exercise manual with access Online YouTube videos (as another option) will be available as examples for proper exercise form for strength training. We will also encourage them to self-monitor weight, dietary intake, and physical activity through MyFitnessPal or paper log. To achieve the retention and provide motivation and strategies for behavioral change in the active control group, participants will receive a Fitbit and the lifestyle modification manual at the end of the study.

C.6 Covid-19 Safety Protocols and Planning

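### For staff-measured outcomes, last value carried forward means baseline carried forward, and no second missing-data analysis accompanies the effect sizes meant for the next trial (minor)

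*Combined protocol and SAP*

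**What the plan says.** Section D.1.b names one approach to missing efficacy data, the "intention to treat principle with last value carried forward approach used to account for data missing due to participant attrition". The model is an ANCOVA adjusting for the baseline value and age. The sample size, 30 intervention and at least 15 control, "accounts for a projected attrition rate of 20" per cent. The attrition is not split by arm.

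Section C.7 fixes the measurement times: "Outcome assessments will be obtained at baseline and 15 weeks later at in-person visits". Section C.3.b gives the same two time points, and Table 3 lists weight, body composition, lipids and inflammatory markers as staff measurements.

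On status and use, section C.1 says "The exploratory outcomes include changes in weight, body composition, lipid profiles, and inflammatory markers", and section D.1.b says "These exploratory analyses will provide effect size estimates to inform the development of a large-scale phase II randomized controlled" weight loss trial. I found no sensitivity analysis for missing outcomes and no stated assumption about outcomes after dropout. Reasons for drop-out are collected, but as a feasibility item.

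**The concern.** With a single post-baseline visit, a participant who misses week 15 has only one staff value to carry forward, the baseline. The analysis then treats a change of exactly zero as if it had been observed. This is one particular assumption about what happens to people who leave, and the plan neither spells it out nor tests it.

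The purpose of these estimates is to size and justify a larger trial. If dropouts in fact keep some of the benefit, the effect handed on is too small and its interval is centred in the wrong place. If the plan used only a missing-at-random analysis, the error could run the other way. One estimate under one assumption does not show the next team how much depends on that choice.

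**Working it through.** **Inputs from the plan (D.1.b).** 30 and 15 participants; 20% attrition, which is 6 and 3 if equal by arm; standardised effects of 0.54 to 0.72.

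**Assumed inputs.** Baseline and week-15 SD of 1; baseline-to-week-15 correlation r = 0.5, 0.7, 0.9; f, the fraction of the completers' between-arm benefit that dropouts keep, from 0 to 1.

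**The plan's own figure.** The plan gives no alpha, power or r for 0.54–0.72. The range is reproduced by 24:12 completers, one-sided 5%, 80% power and the noncentral t distribution: 0.719 at r = 0.6 and 0.539 at r = 0.8. Two-sided 5% with 30:15 comes close (0.73 and 0.54), so the basis cannot be identified. I use 0.72 and 0.54 only as example completers' effects.

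**Step 1: general formula.** Let the completers' change be c in control and c + D in intervention, with dropout fractions p_C and p_T. The carried-forward difference is

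(1 − p_T)(c + D) − (1 − p_C)c.

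**Step 2: equal dropout of 20%.** The c terms cancel and leave 0.8D: 0.8 × 0.72 = 0.576 and 0.8 × 0.54 = 0.432. The true effect over all randomised participants is D(0.8 + 0.2f).

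| f | Truth, D = 0.72 | Carried forward (0.576) | Missing at random (0.72) |
|---|---|---|---|
| 0 | 0.576 | correct | 25% high |
| 0.5 | 0.648 | 11% low | 11% high |
| 1 | 0.720 | 20% low | correct |

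For D = 0.54 the truths are 0.432, 0.486 and 0.540, with the same percentages.

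**Step 3: interval coverage.** Simulation of ANCOVA on arm, baseline and age, 6,000 trials per cell, r = 0.5 to 0.9, nominal 95%:

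| f | Carried forward | Observed data |
|---|---|---|
| 0 | 95–98% | 86–93% |
| 0.5 | 95% | 92–95% |
| 1 | 87–93% | 94–95% |

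**Step 4: unequal dropout.** Keep 9 dropouts in total, D = 0.72, an assumed control change c = 0.2, and dropouts keeping their full change (truth 0.72).
- 9 intervention, 0 control: 0.7 × 0.92 − 0.2 = 0.444, a bias of about 0.28 SD.
- 3 intervention, 6 control: 0.9 × 0.92 − 0.6 × 0.2 = 0.708, almost no bias.

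**Step 5: next-trial size.** Two-sample t test, 80% power, two-sided 5%, SD held at 1.
- Carried forward: 0.576 needs 49 per arm and 0.432 needs 86. Dropout has already diluted these effects, so they count everyone randomised.
- Missing at random: 0.72 needs 32 completers and 0.54 needs 55. With 20% attrition, 32/0.8 = 40 and 55/0.8 = 68.75, so 69 randomised.

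The like-for-like contrast is therefore 49 versus 40, and 86 versus 69.

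**Step 6: standardising by the SD of change.** Carrying baseline forward also shrinks this SD. At r = 0.5 the completers' variance of change is 2(1 − r) = 1. With no control change, the carried-forward variance is 0.8 + 0.16 × 0.72² = 0.883 in intervention and 0.8 in control, an average of 0.841 (SD 0.917). Then 0.576/0.917 = 0.628, which needs 41 per arm (42 if the variances are weighted 2:1), against 40. For 0.54 it is 71 against 69. At r = 0.7 the contrasts are 26–27 versus 25 and 44 versus 43; at r = 0.9, 11–12 versus 10 and 17–18 versus 15. The gap is 1 to 3 per arm.

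**The case against.** The case for leaving the plan alone has weight. The method is named, and assuming that dropouts gain nothing is defensible in a weight loss trial. The outcomes are exploratory. Under equal dropout the largest bias, 0.72 − 0.576 = 0.144 SD, is about half the pilot's standard error of 0.27 at r = 0.5. Missing-at-random multiple imputation had the higher root-mean-square error in 16 of 18 scenarios, so it is not a better single choice. All this stands, and it is why the proposal is to add an analysis and not to replace one.

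Some stronger readings are tempting but not supported:
- *Carried forward is unbiased only if dropouts return to baseline.* Not for the between-arm difference: under equal dropout any change common to dropouts in both arms cancels. What matters is whether they keep a between-arm benefit.
- *The next trial would be sized at 49 instead of 32.* This compares everyone randomised with completers only (Step 5).
- *The true effect always lies between the two analyses.* This can be said, on average, only with similar dropout by arm and f between 0 and 1. The plan gives neither.
- *Home weights may be carried forward, differently by arm.* For intervention, section C.4.d says "Participants will learn how to conduct self-measurements and record body weight each week"; for controls, section C.5 says "We will also encourage them to self-monitor weight, dietary intake, and physical activity through MyFitnessPal or paper log". But section C.7 and Table 3 define outcome weight as a blinded staff measurement, so a clarifying phrase is enough.
- *The plan names two models at once.* The label in D.1.b is loose, but the stated adjustment for baseline and age identifies an ANCOVA.

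**Conclusion.** The point holds as a minor one. That carried forward equals baseline carried forward for staff-measured outcomes follows directly from the two-visit schedule, and no second missing-data analysis is planned. At the projected 20% attrition, equal by arm, the estimate is 0.80 times the completers' effect. The error is between zero and 20% of the true effect, depending on how much benefit dropouts keep, with coverage of about 87–93% at the unfavourable end. With unequal dropout the bias can be about twice as large or nearly vanish. For planning the next trial, the choice matters by at most about 9 per arm at 0.72 and 17 per arm at 0.54 under equal dropout, and by 1 to 3 per arm if effects are standardised by the SD of change.

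These sizes rest on the assumed r, f, dropout splits and control change; the plan gives none of them. The primary feasibility and acceptability outcomes are not affected. The documents do not show that the planned method is wrong, only that its result depends on an untested assumption.

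**What to change.** In section D.1.b:

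1. Keep baseline carried forward, and say that the carried value is the staff-measured baseline.
2. Report beside it an ANCOVA of the week-15 value on arm, baseline and age under missing at random, using observed data or multiple imputation.
3. Adjust both analyses for randomisation wave, since section C.3.d randomises in 4–5 waves.
4. Show dropout by arm.
5. Give both estimates when sizing the next trial, each with its own attrition allowance: none added to the carried-forward effect, which is already diluted, and the expected attrition added to the missing-at-random effect. Do not describe the pair as bracketing the truth unless dropout is similar by arm.

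The cost is a few lines of text, a little programming and 3–4 degrees of freedom for wave. The second estimate has a wider interval: at r = 0.5 its standard error is about 0.31 (observed data) to 0.33 (multiple imputation), against 0.27. Those figures are before wave adjustment, which was not simulated. Imputing within arm would rest on about 12 control completers, so the observed-data ANCOVA is the simpler option. No extra participants or visits are needed.
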